5.5.2 Sponsor Follow-Up

For serious adverse events, adverse events of special interest, and pregnancies, the Sponsor or a designee may follow up by telephone, fax, electronic mail, or a monitoring visit to obtain additional case details and outcome information (e.g., from hospital discharge summaries, consultant reports, or autopsy reports) in order to perform an independent medical assessment of the reported case.

5.6 POST-STUDY ADVERSE EVENTS

Following the Adverse Event Reporting Period (see Section 5.3.1), the investigator does not need to actively monitor patients for adverse events. The Sponsor should be notified if the investigator becomes aware of any serious adverse event that occurs after the end of the adverse event reporting period, if the event is believed to be related to prior study drug treatment.

The investigator should report the event directly to Roche Safety Risk Management via telephone or via facsimile using the Serious Adverse Event/Adverse Event of Special Interest Reporting Form.

5.7 EXPEDITED REPORTING TO HEALTH AUTHORITIES, INVESTIGATORS, INSTITUTIONAL REVIEW BOARDS, AND ETHICS COMMITTEES

The Sponsor will promptly evaluate all serious adverse events and adverse events of special interest against cumulative product experience to identify and expeditiously communicate possible new safety findings to investigators, IRBs, IECs, and applicable health authorities based on applicable legislation.

To determine reporting requirements for single adverse event cases, the Sponsor will assess the expectedness of these events using the following reference documents:

- Lebrikizumab IB
- Pirfenidone Core Safety Information (approved labels)

The Sponsor will compare the severity of each event and the cumulative event frequency reported for the study with the severity and frequency reported in the applicable reference document.

Reporting requirements will also be based on the investigator's assessment of causality and seriousness, with allowance for upgrading by the Sponsor as needed.

6. STATISTICAL CONSIDERATIONS AND ANALYSIS PLAN

The analysis of data from the placebo-controlled period *for each cohort* will be performed when all patients have either completed the *end of the placebo-controlled treatment (Week 52/EOT)* visit or discontinued early from the study. Treatment assignment will be unblinded to the personnel performing the analysis when all data through the EOT visit are in the database and the data have been cleaned and verified *for each cohort*.

The analysis of complete data for the study, including data from the placebo-controlled period, open-label extension period for Cohort A, and the 14-week safety follow-up period, will be performed when all patients have either completed the placebo-controlled period, open-label extension period for Cohort A, and 14-week safety follow-up period or discontinued early from the study, all data from the study are in the database, and the database is locked. *An interim futility analysis of Cohort B was conducted (see Section 6.8).*

Aggregate results of the placebo-controlled period analysis, summarized by treatment arm, may be reported to the public before completion of the study. However, patients and study site personnel will remain blinded to individual treatment assignment until after the study is completed (after all patients have either completed the placebo-controlled period, open-label extension period for Cohort A, and 14-week safety follow-up period or discontinued early from the study), the database is locked, and the study analyses are final.

Detailed specifications of the statistical methods will be described in the Statistical Analysis Plan (SAP).

6.1 DETERMINATION OF SAMPLE SIZE

In Cohort A, a sample size of 75 patients in each treatment group will provide *approximately 80% power to detect a change in the annualized rate of decline in percentage of predicted FVC over 52 weeks of a 3.7% difference in the means of the absolute change from baseline in percentage of predicted FVC at 52 weeks, assuming*

that the common standard deviation is 8% (as reported in the placebo group in the ASCEND trial of pirfenidone) using a two group t-test with a 0.05 two-sided significance level.

In Cohort B, a sample size of 165 patients in each treatment group will provide *approximately* 80% power to detect a 2.5% difference in the *annualized rate of decline* in percentage of predicted FVC *over* 52 weeks, assuming that the common standard deviation is 8% (as reported in the ASCEND trial of pirfenidone) using a two group t-test with a 0.05 two-sided significance level.

6.2 SUMMARIES OF CONDUCT OF STUDY

The number of patients randomized will be tabulated by study site and treatment arm. Patient disposition (the number of patients randomized, treated, and completing each study period) will be tabulated by treatment arm. Premature treatment discontinuation and study discontinuation as well as reasons for discontinuations will be summarized. Eligibility criteria deviations and other major protocol deviations will be summarized.

6.3 SUMMARIES OF TREATMENT GROUP COMPARABILITY

Demographic and baseline characteristics such as age, sex, race/ethnicity, concomitant IPF medication use, comorbid illnesses, and pulmonary function, will be summarized for all randomized patients by treatment arm and perioestin group with use of descriptive statistics. Exposure to study treatment (number of study drug treatments and duration of treatment) will be summarized by treatment arm and study period.

6.4 EFFICACY ANALYSES

The analysis of data from the treatment period in Cohort A will be performed when all patients enrolled in Cohort A have either completed the end of placebo controlled treatment visit (Week 52), or discontinued early from the study. Treatment assignment will be unblinded to the personnel performing the analysis when all data through the Week 52 visit are in the database and the data have been cleaned and verified.

The analysis of data from the treatment period in Cohort B will be performed when all patients enrolled in Cohort B have either completed the end of treatment visit (Week 52) or discontinued early from the study. Treatment assignment will be unblinded to the personnel performing the analysis when all data through the Week 52 visit are in the database and the data have been cleaned and verified.

However, the Sponsor study team directly involved in the study conduct (medical monitoring, clinical operations, drug safety, etc.) will not have access to individual treatment assignments until study completion (*see Section 3.1.3*), when all patients have completed the safety follow-up or discontinued the study. All non-Sponsor personnel who are involved in the conduct of the study (e.g., patients, site monitors, and

investigators) will remain blinded to patient-specific treatment assignments until all patients complete the safety follow-up period or discontinue from the study.

Complete details of the analysis will be provided in the SAP, which will be finalized prior to unblinding the data.

6.4.1 Primary Efficacy Endpoint

The primary efficacy endpoint is *annualized rate of decrease in percentage of predicted FVC (% FVC/year) through Week 52.*

The annualized rate of decrease in percentage of predicted FVC will be compared across the treatment arms with the use of a random slope model on observed cases at a 0.05 two-sided significance level.

The statistical model is as follows:

$$FVC_{ijk} = (\beta_0 + \beta_{0k}) + (a_i * \beta_1 + \beta_{1k}) * t_k + \eta_k + \varepsilon_{ijk}$$

where FVC_{ijk} is the predicted FVC for k th patient at visit j in treatment group i ; β_0 is the intercept; a_i and β_1 is the interaction term of the treatment effect ($i = \text{lebrikizumab or placebo}$) and the slope; t_k is the assessment time (continuous in year) for patient k ; η_k is the effect of baseline lung function (defined as $FVC < 50\%$ vs. 50% to 75% vs. $> 75\%$ predicted) for the k th patient; β_{0k} and β_{1k} are the random components for intercept and slope; ε_{ijk} is the random error for k th patient at time j ; β_{0k} , β_{1k} and ε_{ijk} are assumed to be independent and normally distributed with mean 0 and variance of σ_0^2 , σ_1^2 and σ_ε^2 respectively.

Note that because of a relatively large number of strata defined by the randomization stratification factors, the analysis will be adjusted only for baseline lung function because baseline FVC may impact the clinical disease course.

From the model, least squares means for the annualized rate of decline in each treatment arm and the difference between the two treatment arms will be provided with 95% CIs. The model implicitly imputes missing data on the basis of a patient's estimated rate of worsening of lung function prior to the study visit discontinuation (i.e., under the assumption that it is missing at random).

6.4.2 Secondary Efficacy Endpoints

The secondary efficacy end points of this study are as follows:

- PFS, defined as the time from study treatment randomization to the first occurrence of any of the following *disease progression or death events*:

Death from any cause

All-cause hospitalization

A decrease from baseline (*relative change*) of $\geq 10\%$ in FVC (L)

- Annualized rate of *decrease* in FVC (mL/year) over 52 weeks
 - Time from randomization to first *occurrence* of a $\geq 10\%$ absolute decrease in percentage in predicted FVC or death from any cause
 - Annualized rate of *decrease* in percentage of predicted DL_{CO} over 52 weeks
 - Annualized rate of *decrease* in the ATAQ-IPF total score over 52 weeks (see [Appendix 5](#) for a description of the instrument)
 - Time from randomization to non-elective hospitalization or death from any cause
 - Annualized rate of *decrease* in the 6MWT distance over 52 weeks
 - Time from randomization to first event of acute IPF exacerbation (*defined below*)
- IPF exacerbation is defined as an event that meets all of the following criteria as determined by the investigator:

Unexplained worsening or development of dyspnea within the previous 30 days

And radiologic evidence of new bilateral ground-glass abnormality or consolidation, superimposed on a reticular or honeycomb background pattern, that is consistent with UIP

And absence of alternative causes, such as left heart failure, pulmonary embolism, pulmonary infection (on the basis of endotracheal aspirate or bronchoalveolar lavage if available or investigator judgment), or other events that lead to acute lung injury (e.g., sepsis, aspiration, trauma, reperfusion pulmonary edema)

- Time from randomization to first occurrence of SGRQ (see [Appendix 5](#) for a description of the questionnaire) worsening (total score) as defined by reaching MID ([Swigris et al. 2010](#)): Total Score =7 or death from any cause
- Time from randomization to death from any cause

All continuous endpoints will be analyzed with the use of the same methodology as the primary endpoint (see previous section) *with specifics for models and summaries specified in the SAP.*

For time to event endpoints, the log rank test stratified by baseline lung function (FVC <50% vs. 50% to 75% vs. >75% predicted) will be used to compare the time to event endpoints between the two treatment arms. Time will be measured relative to the date of randomization (Day 1). Patients who do not experience the event will have their data censored on the last date during the placebo-controlled period when, on the basis of the assessments in accordance with this protocol, the patient can be considered to have been event-free. Any patients who undergo lung transplantation will be censored at the date of the transplant. Sensitivity analyses will be provided with lung transplant counted as an event for PFS and time from randomization to death or non-elective hospitalization from any cause.

The primary efficacy assessments for the randomized placebo-controlled period are made on the study day of initiation of the open-label lebrikizumab through Week 52. Assessment on this day will be included for analyses of the randomized placebo-controlled period, but subsequent assessment during the open-label period or after Week 52 will be excluded.

The hazard ratio and its 95% CI will be estimated with the use of a Cox regression model stratified by baseline lung function. In fitting the Cox model, ties will be handled with the approximate likelihood method of Efron (1977). Kaplan-Meier curves will be provided.

Summary statistics of the *ATAQ-IPR* and *SGRQ* endpoints and the changes from baseline will be calculated at each assessment time-point for each treatment group. The mean, standard error, and median of the absolute scores and the mean changes from baseline (and 95% CIs) between treatment groups will be reported for the endpoint. For scores involving change from baseline, patients without baseline values will be excluded from the analyses. Line charts depicting the means and mean changes of subscales over time will be also provided. Scoring for the questionnaire will be based on relevant user manuals.

Frequencies and percentages of missing data for the *ATAQ-IPR* and *SGRQ* endpoints will be compared between the two treatment arms.

Additional details for summarization, sensitivity analyses, and type I error control are provided in the SAP.

6.5 SAFETY ANALYSES

Safety analyses will be based on all patients who received at least one dose of *randomized* study drug, with patients grouped according to the actual treatment received. Safety summaries will be presented by treatment arm for all treated patients. *In addition, safety listings will be provided for any events reported during pirfenidone exposure prior to randomization.*

Safety will be assessed through the summary of adverse events, laboratory test results, (including antibodies to lebrikizumab), ECG, and vital signs. These summaries will be produced separately for *each cohort* for the treatment period (placebo-controlled study treatment period, the *Cohort A* open-label lebrikizumab period).

6.5.1 Adverse Events

Verbatim descriptions of treatment-emergent adverse events will be coded and their incidence summarized by treatment arm.

A treatment-emergent adverse event is defined as any new adverse event reported or any worsening of an existing condition reported on or after the first dose of study drug.

In addition, separate summaries will be generated for serious adverse events, deaths, and adverse events leading to discontinuation of study drug.

Analyses will be performed by treatment group for events of special interest that include anaphylactic reactions, local injection-site reactions, infections, and malignancies:

- *Anaphylactic reactions will be reviewed and adjudicated by independent, external experts accordingly to a charter.*
- *Local injection-site reactions will be identified with the use of the MedDRA high-level term of "injection site reaction".*
- *Infections, as identified with the use of the MedDRA system organ class of "infections and infestations"*
- *Malignancies, as identified on the basis of the MedDRA SMQ of "Malignancy" and the subSMQ of "Malignant and unspecified tumours"*

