4.2 METHOD OF TREATMENT ASSIGNMENT AND BLINDING

Patients will be randomized to the treatment arms through the interactive voice/Web-based response system (IxRS). After written informed consent has been obtained, all patients will receive a screening number, which will be assigned by the IxRS. Following completion of the screening period and after all patient eligibility requirements are confirmed on Day 1, patients will be assigned an identification number (a different number from the screening number) and will be randomized in a 1:1 ratio to one of two treatment arms (**Cohort A** - lebrikizumab 250 mg SC or placebo SC every 4 weeks; **Cohort B** - lebrikizumab 250 mg SC and pirfenidone \leq 2403 mg/d or placebo SC every 4 weeks and pirfenidone \leq 2403 mg/d) for the 52-week placebo-controlled study period. Patients will be randomized on the same day that treatment is to be initiated (Day 1, Visit 2). Dynamic hierarchical randomization will be performed centrally and stratified by region (United States, Europe/Canada, other), lung function (FVC $<$ 50%, 50% to 75%, $>$ 75% predicted), and serum periostin concentration ($<$ 50 ng/mL, \geq 50 ng/mL) within each cohort. During the placebo-controlled study period and the open-label lebrikizumab treatment period, the IxRS will make study treatment kit assignments. IxRS will also make pirfenidone treatment kits available for patients in Cohort B. At each dosing visit during the placebo-controlled period, study treatment kits will be assigned for administration. The placebo and active kits are filled and packaged to look identical. Patient randomization and the study treatment kit assignments will be verified on an ongoing basis by an external and independent statistical coordinating center to ensure that randomization and kit assignments are conducted correctly by the IxRS.

Patients, all study site personnel, and the Sponsor and its agents (with the exception of the IxRS service provider, the external independent statistical coordinating center responsible for verifying patient randomization and study treatment kit assignments, PK/PD laboratory personnel, the iDMC and iDCC members) will be blinded to treatment assignment throughout the placebo-controlled period. As described in Section 6, treatment assignment will be unblinded to the personnel performing the analysis when all data for the primary endpoint period are in the database and the data have been cleaned and verified. [REDACTED]

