5.1.4.3 Gastrointestinal Disorders

In the clinical studies, gastrointestinal events of nausea, diarrhea, dyspepsia, vomiting, gastro-esophageal reflux disease, and abdominal pain were more frequently reported by patients in the ESBRIET treatment groups than in those taking placebo. Dosage reduction or interruption for gastrointestinal events was required in 18.5% of patients in the 2403 mg/day group, as compared to 5.8% of patients in the placebo group; 2.2% of patients in the ESBRIET 2403 mg/day group discontinued treatment due to a gastrointestinal event, as compared to 1.0% in the placebo group. The most common ($>2\%$) gastrointestinal events that led to dosage reduction or interruption were nausea, diarrhea, vomiting, and dyspepsia. The incidence of gastrointestinal events was highest

early in the course of treatment (with highest incidence occurring during the initial 3 months) and decreased over time. Dosage modifications may be necessary in some cases of gastrointestinal adverse reactions.

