5.3.1 Adverse Event Reporting Period

Investigators will seek information on adverse events at each patient contact. All adverse events, whether reported by the patient or noted by study personnel, will be recorded in the patient's medical record and on the Adverse Event eCRF.

After informed consent has been obtained **but prior to initiation of study drug**, serious adverse events caused only by a protocol-mandated intervention should be reported (e.g., serious adverse events related to procedures such as biopsies or spirometry) or protocol mandated washout of medications. See Section 5.4.2 for reporting requirements of Serious Adverse Events.

After initiation of study drug, all adverse events, regardless of relationship to study drug, will be reported until study completion. After this period, the investigator does not need to actively monitor patients for adverse events. Once the study has ended the Sponsor should be notified if the investigator becomes aware of any serious adverse events and adverse events of special interest (see Section 5.6).

For Cohort B only: Safety findings should be reported for patients who are administered background pirfenidone by their health care provider. Safety findings should be collected as of date of consent for the study for patients who are naive to pirfenidone treatment. Safety findings should be collected on the dates when pirfenidone is taken (see Section 4.5.10).

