4.7 SAFETY ANALYSES

Safety analyses will be based on all patients who received at least one dose of randomized study drug, with patients grouped according to the actual treatment received. Safety summaries will be presented by treatment arm for all treated patients. In addition, safety listings will be provided for any events reported during pirfenidone exposure following informed consent on this study but prior to randomization.

Safety will be assessed through the summary of AEs, laboratory test results (including antibodies to lebrikizumab), ECG, and vital signs. These summaries will be produced separately for each cohort for the treatment period (placebo-controlled study treatment period including safety follow-up period for Cohort B patients or Cohort A patients not entering open label extension period and Cohort A open-label lebrikizumab period including the subsequent safety follow-up period).

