4.7.2 Adverse Events

Verbatim descriptions of treatment-emergent adverse events (TEAEs) will be coded with use of the latest version of Medical Dictionary for Regulatory Activities (MedDRA) dictionary, and their incidence summarized for each treatment arm by system organ class (SOC) and preferred term. A TEAE is defined as any new AE reported, or any worsening of an existing condition reported on or after the first dose of study drug. In addition, separate summaries will be provided for TESAEs, deaths, and AEs leading to discontinuation of study drug.

Analyses will be performed by treatment group for events of special interest that include anaphylactic reactions, local injection-site reactions, infections, and malignancies.

- Anaphylactic reactions will be reviewed and adjudicated by the iACC.
- Local injection-site reactions will be identified with use of the MedDRA high-level term of “injection site reaction”.
- Infections, as identified with use of the MedDRA SOC of “infections and infestations”.
- Malignancies, as identified on the basis of the Standardized MedDRA Queries (SMQ) of “Malignancy”.

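### Treatment-emergent events are defined by when they are reported, not when they begin, so in Cohort B some pirfenidone run-in events can be counted as emergent on lebrikizumab or placebo

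*Combined protocol and SAP*

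**What the plan says.** Protocol 6.5.1 defines a treatment-emergent adverse event as "any new adverse event reported or any worsening of an existing condition reported on or after the first dose of study drug". SAP 4.7.2 has "any new AE reported, or any worsening of an existing condition reported on or after the first dose of study drug". SAP section 1 says that the SAP supersedes the protocol on the analysis plan, so the SAP wording governs, and it makes no change of substance. In both, the only time anchor is reporting relative to the first dose. Onset date, pre-dose severity and the order of events within Day 1 are not mentioned.

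Events from the pirfenidone run-in get separate treatment. Protocol 6.5 says that "safety listings will be provided for any events reported during pirfenidone exposure prior to randomization". SAP 4.7 narrows this to "any events reported during pirfenidone exposure following informed consent on this study but prior to randomization". Both again use reporting as the criterion.

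On collection, Protocol 5.3.1 states for Cohort B: "Safety findings should be collected as of date of consent for the study for patients who are naive to pirfenidone treatment". It also asks investigators to enquire about adverse events at every contact. Protocol 4.2 puts randomization and the first injection on the same day, Day 1 (Visit 2).

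**The concern.** An event can begin during the run-in and be reported only on or after the day of the first injection. Under the stated rule it may then appear in the Cohort B emergent-event tables, although it began before any randomized drug. It would also miss the pre-randomization listing, because it was not reported before randomization.

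The events at risk are those that pirfenidone itself causes. Protocol 5.1.4 names gastrointestinal, skin and liver events, and 5.1.4.3 describes the gastrointestinal events as early, "with highest incidence occurring during the initial 3 months". Comparing lebrikizumab with placebo on a pirfenidone background is a stated safety objective (Protocol 2.2). Events that predate randomization carry no information about that comparison. Adding them to both arms makes the arms look more alike.

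**Working it through.** The plan gives no figure on this point, so there is none to reproduce. The check sets the collection schedule against the rule and then works out direction and possible size.

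**Step 1: when run-in events are asked about.** Protocol 4.5.17.1 identifies Visit 1.5 as the start of the run-in. Appendix 3 marks adverse events at Visits 1, 1.5 and 2, with no scheduled visit between 1.5 and 2, an interval of 28 to 42 days. After pirfenidone starts, the next scheduled enquiry is therefore Visit 2, the day of the first injection.

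**Step 2: apply the rule to one case.** Suppose nausea begins in the second week of the run-in.

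- Reported at an unscheduled contact before Day 1: before the first dose, in the listing, not emergent.
- Reported at Visit 2 before the injection: before the dose by clock time, on the day of the dose by calendar date. The rule does not say which applies.
- First mentioned at Visit 3 (Week 1): reported after the first dose, so emergent on the reporting criterion, and outside the listing.

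Only the first case is settled by the text.

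**Step 3: direction.** Let m be the share of patients in each arm counted as having an event only because a run-in event was misclassified. It breaks down as m = f × r × s, where f is the share who had the run-in, r is the chance of a run-in event of the given type, and s is the share of those events that pass through as emergent. Randomization makes m the same in both arms on average. If run-in and later events are independent, a true rate p is observed as

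p′ = m + (1 − m)p.

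The risk difference becomes (1 − m)(p₁ − p₀), and the risk ratio moves toward 1.

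**Step 4: possible size.** The documents give none of f, r or s. With assumed true rates of 30% and 20%:

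| m | Observed rates | Risk difference (points) | Risk ratio |
|---|---|---|---|
| 0 | 30.0% vs 20.0% | 10.0 | 1.50 |
| 0.05 | 33.5% vs 24.0% | 9.5 | 1.40 |
| 0.10 | 37.0% vs 28.0% | 9.0 | 1.32 |
| 0.20 | 44.0% vs 36.0% | 8.0 | 1.22 |
| 0.40 | 58.0% vs 52.0% | 6.0 | 1.12 |

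For example, at m = 0.05 the rates are 0.05 + 0.95 × 0.30 = 0.335 and 0.05 + 0.95 × 0.20 = 0.240, a ratio of 1.40. The share s matters: f = 0.5 and r = 0.4 give m = 0.20 if every run-in event is misclassified (s = 1), m = 0.05 if a quarter are (s = 0.25), and m = 0 if none are.

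**The case against.** A reader might infer that every run-in event asked about on Day 1 counts as emergent. The documents do not support that. A note to Appendix 3 puts all assessments on treatment days before dosing unless otherwise specified, and no exception is made for the adverse event enquiry. SAP 4.7.4 takes the Visit 2 pre-dose value as baseline for vital signs. The definition also requires an event to be new or a worsening, and a condition already present before the injection can fairly be read as neither. SAP 4.7.1 takes study drug to mean lebrikizumab or placebo, so the first pirfenidone dose is not the reference.

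Nor will all run-in events wait until Day 1. Enquiry is made at every contact (5.3.1), run-in patients are monitored for tolerability (4.3.4), pirfenidone dose changes are recorded (5.1.4), and unscheduled visits are allowed at any time (4.5.17.5). The more troublesome events are likely to surface earlier.

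It is also tempting to say that every Cohort B rate would rise. Injection-site reactions cannot precede the first injection. Antibiotic-treated infection during screening or run-in, and known current malignancy, are exclusions (4.1.2). Lebrikizumab's own events of special interest are therefore largely untouched.

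Finally, the 3-month gastrointestinal window is about 13 weeks (52/4). The run-in covers 4/13 to 6/13 of it, roughly 31% to 46%, and the rest follows randomization.

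These points stand, and they limit the problem. They do not remove it. The rule has no pre-dose criterion for Day 1, *new* is undefined, and nothing above covers an event first mentioned after Day 1. The listing is not said to exclude its events from the emergent tables, and it uses the same anchor.

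**Conclusion.** The point holds as a definition that can misclassify, in one cohort and mainly for one family of events. It affects Cohort B patients who had the run-in, chiefly for gastrointestinal, skin and liver events. The effect falls equally on both arms, and its direction is toward no difference.

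Its size cannot be derived from the documents and may be near zero. The table in the working rests on assumed true rates, an assumed range for m, and independence of run-in and later events. It shows direction and scale, and is not an estimate for this trial.

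A reader might go further and describe a loss of power. The emergent-event analysis is a descriptive summary of incidence with no planned safety test, so power is not a property of this part of the plan. It has also not been shown that the Cohort B comparison is biased in fact. The change is worth making because it is cheap and serves a stated safety objective.

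**What to change.** Before Cohort B is unblinded, amend SAP 4.7.2, and Protocol 6.5.1 to match:

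- Define a treatment-emergent event as one with onset, or with worsening over its pre-dose severity, at or after the first injection of lebrikizumab or placebo.
- State a default for events that begin on Day 1 with no recorded order relative to the injection. Counting them as emergent is the cautious convention. Once onset is the criterion, this touches only events that began on that calendar day.
- In SAP 4.7 and Protocol 6.5, define the run-in listing by onset between the first pirfenidone exposure after consent and the first randomized dose.

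The cost is a sentence in each place plus the default. Protocol 5.3.5.1 already refers to a starting date on the adverse event form, so the onset criterion appears to need no new data. There are two drawbacks. The Day 1 assignment is a convention and will sometimes be wrong. Protocol 5.3.5.3 describes fields for initial and most extreme intensity without mentioning a date for the change, so the form should be checked and a rule stated for persisting run-in events whose worsening cannot be dated.
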